7.3.2.1. Medical record review of primary and secondary outcomes

At each annual monitoring query, for the evaluation of primary outcomes (i.e., GBS and ADEM), screening for potential events in the administrative claims data of the RPs will be done using the case-finding algorithms described in Table 4. Once each annual monitoring query is complete, given the rarity of GBS and ADEM, we will immediately seek to obtain the medical records of all patients identified as having possible events

based on our algorithms, abstract the data necessary to confirm these diagnoses from the medical records obtained, and implement a formal adjudication process with a team of expert clinicians, preferably neurologists, to confirm these events. Only confirmed cases will be included in the final primary analyses. For those outcomes, timing of symptom onset will be discerned from medical record review and timing of the event will be classified based on expert clinician adjudication (i.e., the date of diagnosis from the claims data will not be used due to concerns with misclassification).

Since AF is a more frequent health outcome in the population of interest compared to GBS and ADEM, a conventional approach will be followed to confirm the validity of the algorithms for each of these outcomes during the initial annual monitoring queries (we anticipate that the sample sizes for each AF validation can be accrued within the first or second annual monitoring periods given the prevalence of AF in the age group of the study population, but will need to assess initial monitoring query results) [Weinstein, 2023]. For the AF outcome, we *a priori* seek to identify an algorithm that has a positive predictive value (PPV) of \geq 80% to provide confidence that identified outcomes are true events. We estimate that 63 patients' charts (complete and adjudicated) would allow determination of the PPV of each case-finding algorithm with a maximum 95% CI of \pm 10%, assuming a PPV of 80% (Table 3).

The number of adjudicated charts needed for the AF validation will be determined based on the number of AF cases identified in the monitoring query(s). We expect to conduct the validation within 1-2 RPs, including the one RP with the most AF events identified during the initial monitoring queries.

Note that for analyses that include claims-based outcomes of interest in the inpatient setting, admission dates will be used, not discharge dates.

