Table 7 ICD-10-CM diagnosis codes for new-onset AF case-finding algorithm

Full Description	Code
Paroxysmal atrial fibrillation	148.0
Unspecified atrial fibrillation	148.91

Validation of New-Onset AF events: Materials for medical record review (including the abstraction and adjudication forms with case classifications and SOPs), will be developed prior to having results from the first monitoring query.

Since AF is a common health outcome among older adults, we will evaluate the PPV (95% CI) of our proposed algorithm for new-onset AF within a random sample of vaccinees who meet the algorithm. Our focus is on PPV because a sufficiently high PPV provides confidence that identified outcomes are true events.

As described in Section 7.3.2.1 above, we will identify a random sample of patients with new-onset AF across our RPs according to the algorithm developed in Table 4 and based on the number of charts needed in Table 3. If we obtain a PPV \geq 80%, it will provide reassurance that majority of new-onset AF events ascertained using the algorithm are true cases and reduce concerns regarding outcome misclassification; a claims data-only analysis will be conducted, possibly including adjustment for the PPV. If, contrary to expectation, the PPV of a coding algorithm is found to be below 80%, the inferential analyses will be restricted to chart-confirmed cases only. In this situation, additional charts will be sought to obtain 69 confirmed cases. This is based on an assumption of an IR between 10 and 50 per 1000 person-years and a RR of 2.

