A trained abstractor will extract specific information from the hospital records onto a structured data abstraction form. The form will collect information from hospital admission notes, hospital discharge summaries, inpatient or outpatient cardiology consultation notes, inpatient or outpatient electrocardiograms (ECG), inpatient or outpatient Holter or event monitors, inpatient or outpatient telemetry strips, and inpatient or outpatient anti-arrhythmic medications administered. Forms will be reviewed by a clinician, preferably a cardiologist. To be considered a confirmed case of AF, there must be evidence of AF on one of the following studies: 1) ECG or rhythm strip, 2) Holter monitor, event monitor, or telemetry, or 3) pacemaker interrogation [Calkins, 2017]. Possible AF will be defined as a clearly noted AF diagnosis recorded by a clinician in the chart in the absence of any arrhythmia monitoring study. Abstractors and adjudicators will be blinded to vaccination date – i.e., they will not know whether the event occurred in the risk or control window.

If an algorithm for AF is validated within the data of a participating RP at the time of study conduct and meets our performance criteria, it will be considered whether to instead apply that algorithm and the protocol and SAP will be updated accordingly.

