7.7.2.3. Sensitivity analyses

Sensitivity analyses will be conducted to assess whether results are robust after addressing concerns related to misclassification or other biases. The analyses are summarized in the protocol and will be detailed in the SAP.

As summarized in Table 4, there will be sensitivity analyses for GBS, ADEM and AF with different risk and control windows.

The primary inferential analyses for GBS and ADEM will be restricted to those cases that are adjudicated as "confirmed" during medical record review. As a sensitivity analysis the same analyses will be conducted but will include cases adjudicated as confirmed or possible based on medical record review. In addition, if charts are not obtainable for all events identified via the claims-based algorithms, a sensitivity analysis will be conducted including chart-confirmed cases plus those patients identified with an outcome of interest whose charts were unobtainable (and excluding those adjudicated as not cases).

As described in Section 7.3.4, there is a potential for confounding due to seasonal trends in both *Arexvy* vaccination and the outcomes of interest. For the GBS and AF inferential analyses, adjustment will be made for seasonality.

For GBS and ADEM, a sensitivity analysis will be conducted excluding patients with evidence of an immunocompromising condition.

For AF, the PPV for the algorithm will be calculated using confirmed cases only as the primary analysis. A sensitivity analysis will also be conducted where both confirmed and possible cases are included in the calculation. In addition, a sensitivity analysis will be conducted where the post-vaccination enrolment requirement is through the control window (Day 16); this is compared to the primary AF analysis where enrolment is required through Day 106, the last day an AF diagnosis code may occur for the algorithm criterium that requires 2 diagnosis codes in the outpatient or ED setting.

For all outcomes, if there are an adequate number of events with evidence of concomitant vaccination, infection, or medication (where concomitant is defined as before, on the same day as, or after *Arexvy* administration), additional analytic possibilities beyond descriptive statistics will be considered.

Any additional analyses will be described in detail in the SAP.

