7.7.3. Secondary analysis/Exploratory analysis

The analysis of new-onset AF, a secondary outcome, will be conducted using the same analytic approach as the primary outcomes described above in Section 7.7.2.1 in terms of the SCRI design as well as identification of fatal events. However, as explained in detail in Section 7.3.2.4, all claims-identified cases will be included for new-onset AF assuming the PPV for the diagnostic coding algorithm is $\geq 80\%$.

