7.9. Limitations of the research methods

There are potential scientific risks and limitations as well as logistical risks to consider.

Sample Size: Adequate sample size will be difficult to achieve if uptake of *Arexvy* is low, since the primary outcomes are rare. To minimize this likelihood, it is proposed to evaluate vaccinees within data from large national RPs.

Confounding: The use of the SCRI design for acute outcomes guards against confounding by many of the covariates that can confound other designs, including chronic disease status. Nonetheless, seasonality can confound SCRI analyses. Assessment of whether there is evidence of seasonality will be done and if so, a sensitivity analysis will be conducted that explicitly adjusts for seasonality. In addition, specifying the optimal risk window can be a challenge and misclassification is possible with respect to timing of the event. To address this, for the primary outcomes of GBS and ADEM, the final inferential analyses will be restricted to chart-confirmed cases using information and the timing of the event (i.e., risk vs control window) will be based on information from the medical record.

Misclassification bias: As in any study that includes administrative claims data, case ascertainment algorithms are rarely perfectly sensitive and specific. As such, we may not identify all potential outcomes of interest and some outcomes will not be true events.GBS and ADEM will be ascertained using full case adjudication. If records are unable to be retrieved for event confirmation, those patients will not be included in the primary analysis. New-onset AF will be ascertained using an algorithm with $\geq 80\%$ PPV. We may perform quantitative bias analyses to assess the impact of outcome misclassification to understand the effect of imperfect specificity and sensitivity on observed effect sizes.

In addition, the death data are expected to be incomplete due to the nature of administrative claims data in the US. There is a time lag in the identification of out-of-hospital deaths in these data sources.

Day-of-the-week effects: Health care utilization is expected to vary by the day of the week, clustering on some days in the week compared to the others. Typically, vaccine safety studies account for potential day-of-the-week effects by using risk and control windows that are multiples of 7 [Yih, 2016b]. Our analyses with risk windows of 8 days and 3 days maybe susceptible to day-of-the-week effects.

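### When the AF algorithm passes its PPV check, events that the study's own adjudicators rejected still count as AF cases (minor; the gain from removing them is modest near 69 cases and negligible at 1,000)

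*Protocol*

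**What the plan says.** Protocol section 7.3.2.1 plans a chart validation of the AF algorithm: "We estimate that 63 patients' charts (complete and adjudicated) would allow determination of the PPV" to within 10 percentage points if the PPV is 80%. Table 3 scales the number of charts to the number of AF cases identified. Section 7.3.2.4 calls for a random sample and adds that "Abstractors and adjudicators will be blinded to vaccination date".

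The result decides the case set:

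- PPV below 80%: "the inferential analyses will be restricted to chart-confirmed cases only" (section 7.3.2.4).
- PPV at least 80%: "a claims data-only analysis will be conducted, possibly including adjustment for the PPV" (section 7.3.2.4). Section 7.7.3 says that "all claims-identified cases will be included for new-onset AF assuming the PPV for the diagnostic coding algorithm is" at least 80%.

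The AF sensitivity analyses in section 7.7.2.3 change which charts count toward the PPV, the enrolment requirement, the windows and the seasonality adjustment. None changes the handling of events adjudicated as not AF. Section 7.9 adds only an option: "We may perform quantitative bias analyses to assess the impact of outcome misclassification".

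For GBS and ADEM, section 7.7.2.3 has a sensitivity analysis that adds events with unobtainable charts to the confirmed ones, "and excluding those adjudicated as not cases".

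**The concern.** By the time of the AF analysis, some algorithm-positive vaccinees will each have been judged not to have AF. In the claims-only branch that judgement feeds the PPV estimate and nothing else, and the same people are then analysed as AF cases. The protocol gives no reason. It does the opposite in the GBS/ADEM analysis that combines reviewed and unreviewed events, and it uses only confirmed AF cases when the PPV is below 80%.

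An event that is not AF carries no information on the AF relative risk. If such events are unrelated to vaccination, they fall about equally in two windows of equal length and move the IRR toward 1. In a safety study, that understates any harm. The two mitigations named, a PPV adjustment and a quantitative bias analysis, are both optional.

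**Working it through.** **Inputs.** From the protocol: equal 8-day windows; two-sided alpha 0.05, power 80%; 69 cases for a relative risk (RR) of 2 (section 7.5, Table 9); PPV threshold 80%; chart numbers in Table 3. Assumed: true RR 2, PPV exactly 80% (the worst case in this branch), false positives split evenly over the windows, and every unconfirmed chart counted as not AF.

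**1. The plan's 69 cases.** Signed-root formula of the cited sample-size method, with equal windows and p = 2/3:

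- A = 2[p ln 2 − ln 1.5] = 0.1133
- B = (ln 2)² p(1 − p)/A = 0.9426
- n = (1.960 + 0.842√B)²/A = 68.09, rounded up to 69.

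The figure reproduces. It is a count of true cases, with no allowance for false positives.

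**2. Dilution with all claims cases kept.** Risk-window share = 0.8 × 2/3 + 0.2 × 0.5 = 0.6333, so IRR = 0.6333/0.3667 = 1.73. At PPV 90% the same formula gives 1.86. At a true RR of 1 it gives 1.00, so there is no bias under the null.

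**3. How many non-cases would be known.** Table 3 at PPV 80% follows n = 63/(1 + 62/N) for N identified cases. This returns 59 at 1,000, 62 at 5,000 and 63 at 10,000 and above, as tabulated. Carried down to smaller N:

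| Claims cases N | Charts | Known non-cases (20%) | IRR, all kept | IRR, known non-cases dropped |
|---|---|---|---|---|
| 69 | 33.2 | 6.6 | 1.73 | 40.38/21.98 = 1.84 |
| 100 | 38.9 | 7.8 | 1.73 | 59.44/32.78 = 1.81 |
| 200 | 48.1 | 9.6 | 1.73 | 121.86/68.52 = 1.78 |
| 1,000 | 59.3 | 11.9 | 1.73 | 627.40/360.73 = 1.74 |

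The last column is (0.8N × 2/3 + u/2)/(0.8N × 1/3 + u/2), where u = 0.2N minus the known non-cases. At N = 69, u = 13.8 − 6.6 = 7.2. At 5,000 cases, known non-cases are about 12.4 of 5,000, or 0.25%.

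**4. Power near the target.** Power = Φ[(√(nA) − 1.960)/√B], with A and B recomputed for the IRR concerned. With 69 claims cases at IRR 1.73 it is about 61%. With 62.4 cases at IRR 1.84 it is about 65%, despite fewer events.

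**5. Would the optional PPV adjustment do the same job?** A single overall PPV multiplies both window counts and cancels: (0.8 × risk)/(0.8 × control) = risk/control. Window-specific PPVs would be needed. In this example they are 0.5333/0.6333 = 84% in the risk window and 0.2667/0.3667 = 73% in the control window, and few charts would estimate them imprecisely.

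**6. Dependence on the even split.** If a share q of false positives falls in the risk window, the risk-window share is 0.5333 + 0.2q. With q = 0.5 the IRR is 1.73, with q = 2/3 it is 2.00 (no bias), and with q = 0.75 it is 2.16 (bias away from 1).

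**The case against.** The strongest objection is size. Table 3 runs from 1,000 to 100,000 AF cases, where removal moves the IRR by about 0.01 or less. Sixty-nine is a minimum, not a cap. At 16.6 per 1,000 person-years and RR 2, 200 true AF cases need about 200/(3 × 0.0166 × 8/365.25) ≈ 183,000 vaccinees, about 1% of the roughly 17.5 million members aged 50 and over listed in section 7.4. Uptake is not stated, so the final count is unknown. This objection stands and is why the point is minor.

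Second, section 7.3.2.4 defines possible AF as a clinician's diagnosis without a monitoring study, and section 7.7.2.3 bases the primary PPV on confirmed cases only. Some unconfirmed charts are therefore not rejected events, so fewer would be removed than the table shows. This also stands.

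Third, validation is expected in one or two research partners, so removal would apply a stricter case definition there than elsewhere. That would matter in a between-person comparison. Here each case is its own control and adjudicators do not know the window, so removal should favour neither window.

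Fourth, the details of a PPV adjustment belong in the SAP. That is fair for the adjustment, but section 7.7.3 already fixes the case set in the protocol.

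A reader might also pair the 63 charts with the 69-case target, giving 12.6 known non-cases and an IRR of 1.97 once they are dropped. The protocol does not support this. Table 3 reaches 63 charts at PPV 80% only from 10,000 cases, and its rule gives about 33 at 69 cases. With about 30% of charts expected to be unobtainable (section 7.3.2.1), only about 48 of 69 could be reviewed at all.

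**Conclusion.** The point holds as an inconsistency with a modest effect. If the PPV is at least 80%, the protocol keeps AF events that its own blinded reviewers have rejected, while its comparable GBS/ADEM analysis excludes such events. At PPV 80% and a true RR of 2, removing them moves the expected IRR from 1.73 to about 1.84 at 69 cases and to 1.74 at 1,000. A higher PPV, or some possible AF among the unconfirmed charts, makes the gain smaller.

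Two stronger readings should be avoided. The pull toward 1 is not a fact of the design. It needs false positives that are unrelated to vaccination and spread about evenly over the windows, and it can vanish or reverse if they cluster early. Nor would removal cure the dilution, since most of it comes from unreviewed false positives, increasingly so as the case count grows. The case for removal is that events known not to be AF do not belong in the AF case set. Severity is minor, and AF is a secondary outcome.

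**What to change.** In sections 7.3.2.4 and 7.7.3, replace the rule that all claims-identified cases enter the analysis with wording such as:

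*If the PPV is at least 80%, the AF analysis includes all claims-identified cases except those whose chart was reviewed and adjudicated as not AF; confirmed and possible AF are kept. Any adjustment for the PPV applies only to cases without an adjudicated chart.*

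Keep the all-claims result as a sensitivity analysis, so that the uniform claims definition is still reported.

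The cost is one linkage of adjudication results to the case file and at most about 13 fewer events (63 × 0.2 = 12.6). No further charts or patients are needed.

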7.2. Study Population and Setting

Information on the 5 participating RPs is described below in Section 7.4.

Members of participating US-based health plans \geq 50 years of age will be eligible for inclusion in the evaluation of each outcome if all of the following criteria are met:

- 1. Evidence of receipt of a single dose *Arexvy*.
- 2. 365 days of continuous medical and pharmacy enrolment, allowing up to 45-days' gap, prior to *Arexvy* receipt.
- 3. For evaluation of GBS and ADEM cases: Continuous enrollment through the end of the respective control interval and extra days except in case of death after *Arexvy* vaccination.
- 4. For evaluation of AF cases: Continuous enrolment through the Day 106 postvaccination, except in case of death after *Arexvy* vaccination.
- 5. For each outcome: First-in-365-days case of the outcome in the risk or control interval (i.e., definition of an incident case).
- 6. No evidence of a second dose of *Arexvy* during the follow-up period.
- 7. No evidence of administration of another medical product indicated for RSV disease prevention (i.e., vaccine from different manufacturer or a monoclonal antibody to prevent RSV lower respiratory tract disease) prior to the index *Arexvy* vaccination or during the follow-up period.

Patients will be required to be enrolled throughout the risk and control windows combined, plus an extra 7 days for GBS and ADEM analyses, and an extra 90 days for AF analysis. This study will include outcomes of interest among people who die during the full window. The number of events, if any, that were among people who died during follow-up will be quantified. See Section 7.7.2.1 for additional details regarding inclusion of those who died in the inferential analyses.

Health plan members eligible for inclusion in research activities, including chart review, will be included.

Illustrations of temporal inclusion criteria for SCRI analyses are shown Figure 1, Figure 2, and Figure 3 below. The red star in each figure indicates occurrence of an outcome of interest.

Figure 1 Illustration of SCRI study design for new-onset GBS and ADEM outcomes

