Number of AF cases identified	1 000	5 000	10 000	20 000	100 000		
Actual PPV	Number	Number of adjudicated charts needed					
60%	86	92	93	93	94		
65%	82	87	88	89	89		
70%	76	81	82	82	82		
75%	69	72	73	73	73		
80%	59	62	63	63	63		
85%	48	50	50	50	50		
90%	35	36	36	36	36		

Table 3Number of charts needed to obtain a 95% two-sided Cl ±10% for
new-onset AF validation*

Abbreviations: AF: atrial fibrillation CI: confidence interval; PPV: positive predictive value.

*The needed sample size for a 2-sided 95% CI for a binomial proportion with a 10% margin of error was calculated using a range of possible AF cases. These calculations were done in Excel.

To account for the fact that approximately 30%, or more, of hospital medical records might not be available to review, we will oversample from a random sample of the total AF cases identified according to the case-finding algorithm to ensure we obtain the target number of charts needed. Once the initial annual monitoring query, which will include new-onset AF, is complete, medical records of patients in the sample will be requested immediately. Once charts have returned, the data necessary to confirm these diagnoses from the medical records will be abstracted, implement a formal adjudication using a team of expert clinicians, preferably cardiologists, to confirm these events, and determine the PPV of the algorithm for new-onset AF.

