Outcome	Diagnosis code(s) to identify event	Event identification care setting and details	Risk window	Control window, Extra days	Look-back period for outcome-free window	Diagnosis code(s), care setting for outcome-free period	Published algorithm data	Chart review considerations
New- onset ADEM	G04.00, G04.01, G04.02 ^b	CCI	Primary: 1-42 days Sensitivity: a) 1-21 days and (b) 8-28 days	Control window: 43-84 days, Extra days: 7	-365 through - 1 (day 0 is the day of the event)	G04.00, G04.01, or G04.02, inpatient setting (any position)	ICD-10-CM based algorithm not available	Will seek charts on all events. Final analysis will include chart- confirmed events only.

220149 (EPI-RSV-041 OA VS US DB) Protocol Amendment 2 Final

Outcome	Diagnosis code(s) to identify event	Event identification care setting and details	Risk window	Control window, Extra days	Look-back period for outcome-free window	Diagnosis code(s), care setting for outcome-free period	Published algorithm data	Chart review considerations
New- onset AF	See Table 7	CCI	Primary: 1-8 days	Primary: 9-16 days	-365 through day -1 (day 0 is day of the	Any indicated AF diagnosis ir Table 7 in any care setting	PPV for ICD-10-CM (I48) based algorithms ranged from 67.5%-	Will aim to review charts from ~63 presumed cases from selected RPs to determine RBV d
			Sensitivity (a): 1-28 days	Sensitivity (a): 29-56 days	event)		75.7% [Chamberlain, 2022]	to determine PPV
			Sensitivity (b): 1-3 days	Sensitivity (b): s4-8 days				
				Extra days: 0				

Abbreviations: AF: atrial fibrillation; ADEM: acute disseminated encephalomyelitis; ED: emergency department; GBS: Guillain-Barré syndrome; ICD-10-CM: International Classification of Diseases, tenth revision, clinical modification; PPV: positive predictive value.

a. GBS ICD-10-CM codes and descriptions:

G61.0: Guillain-Barré syndrome

G65.0: sequelae of Guillain-Barré syndrome

b. ADEM ICD-10-CM codes and descriptions:

G04.00: Acute disseminated encephalitis and encephalomyelitis, unspecified G04.01: post-infectious acute disseminated encephalitis and encephalomyelitis, G04.02: Postimmunization acute disseminated encephalitis, myelitis, and encephalomyelitis.

Note that for AF, if the first qualifying diagnosis code occurs on Day 16, then the last possible second code would be on Day 106.

d. The final number of complete, adjudicated charts needed for AF will be based on the number of AF cases identified, as summarized in Table 3.

C.

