7.3.2.4. Ascertainment and Confirmation of New-Onset AF Events

Screening for New-Onset AF: Within each RP's database, patients will be identified as having new-onset AF within 16 days after *Arexvy* vaccination if they had:

unpublished data on post-marketing adverse events reported to GSK through August 2024, which had a maximum time to onset of 8 days post-vaccination.

In one sensitivity analysis, our risk and control windows will be 1-28 days and 29-56 days respectively. This is based on: (i) the available evidence from literature on risk intervals for cardiac arrythmias after vaccination in older adults [Patone, 2022a; Patone, 2022b], and (ii) data from the Phase 3 efficacy trial which indicated that all new-onset serious AF events occurred within 28 days after vaccination (only serious reports are considered as they represent the events for which the participants were hospitalized due to their AF onset and only such reports would be captured in this study design) [GSK, 2023]. Further, using 28 days (versus, for example, 30 days) avoids potential day-of-week bias [Yih, 2016b]. In another sensitivity analysis, we will use risk and control windows of 1-3 days and 4-8 days respectively, since unpublished post-marketing reports have indicated a maximum time to onset of 3 days.

Of note, health care utilization is expected to vary by the day of the week, clustering on some days in the week compared to the others. Typically, vaccine safety studies account for potential day-of-the-week effects by using risk and control windows that are multiples of 7 [Yih, 2016b]. Our analyses with risk windows of 8 days and 3 days may be susceptible to day-of-the-week effects.

The date of the event will be the date of the first qualifying AF diagnosis if there are two outpatient codes. Continuous enrolment through Day 106 post-vaccination will be required for the primary AF inferential analysis, ensuring vaccinees have equal time to acquire a second diagnosis for AF in the outpatient/ED setting. The final analysis will include individuals who have AF and die during follow-up. We will also conduct a sensitivity analysis where continuous enrolment is required only through the control window (Day 16).

Arexvy vaccinees identified with AF via the claims-based algorithm will be assessed for a prior AF diagnosis code >365 days before the event date. The number of AF events meeting this criterion will be reported for each risk and control window combination.

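### The 80% PPV gate is set for new-onset AF, but chart confirmation checks only that AF is present, so earlier AF that passes the two-code, 365-day look-back can count as confirmed

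*Protocol*

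**What the plan says.** **Purpose of the validation.** Section 7.3.2.1 says that chart review will "determine the PPV of the algorithm for new-onset AF". Section 7.3.2.4 repeats this: "we will evaluate the PPV (95% CI) of our proposed algorithm for new-onset AF within a random sample of vaccinees". If the PPV is at least 80%, the claims cases are analysed, possibly with adjustment for the PPV. If it is lower, only chart-confirmed cases are analysed, and charts are sought until 69 are confirmed.

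**Chart rule.** Section 7.3.2.4: "To be considered a confirmed case of AF, there must be evidence of AF on one of the following studies". The list is ECG or rhythm strip; Holter, event monitor or telemetry; pacemaker interrogation. The weaker category is also about presence only: "Possible AF will be defined as a clearly noted AF diagnosis recorded by a clinician in the chart in the absence of any arrhythmia monitoring". Section 7.7.2.3 computes the primary PPV from confirmed cases and a sensitivity version from confirmed plus possible cases.

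**Incidence rule.** Section 7.2, criterion 5: "First-in-365-days case of the outcome in the risk or control interval". For AF, Table 4 applies this to the Table 7 codes, in every care setting, over days -365 to -1 before the event. Table 7 ("ICD-10-CM diagnosis codes for new-onset AF case-finding algorithm") holds two codes, paroxysmal AF and unspecified AF.

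**Longer look-back.** Cases found by the claims algorithm "will be assessed for a prior AF diagnosis code >365 days before the event date". The number is reported for each pair of windows. No exclusion or sensitivity analysis is attached to it.

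**The concern.** The outcome has two parts: AF is present, and it is new. Chart review checks the first part only. The second is left entirely to claims, and the validation that should test the claims rule cannot see its failures on this point.

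Two groups can pass: patients whose AF in the prior year was coded only outside Table 7, and patients whose last AF code is more than 365 days old. If a tracing shows AF, both are confirmed. They stay in the claims branch because the gate counts them as true positives, and in the chart-confirmed branch because the same rule selects the cases. Any PPV adjustment would use a PPV for AF rather than for new-onset AF.

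The plan handles its other outcomes differently. For GBS and ADEM the adjudicator records symptom onset from the chart (Sections 7.3.2.2 and 7.3.2.3), whereas the AF event date is the claims date. For GBS the outcome-free screen is wider than the event code (G61.0 or G65.0 against G61.0 alone). For AF the two lists are the same.

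The gate may also be close. The PPVs that Table 4 cites for I48-based algorithms run from 67.5% to 75.7%, all below 80%.

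**Working it through.** **1. The plan's own figures.** Inputs from Sections 7.3.2.4 and 7.5: RR 2, two-sided alpha 0.05, power 80%, equal windows (r = 0.5). I used the signed-root likelihood-ratio formula for self-controlled designs, with d = RR·r + 1 − r:

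- A = 2[(RR·r/d)·ln RR − ln d] = 2[(2/3)(0.6931) − 0.4055] = 0.1133
- B = (ln RR)²/A × RR·r(1 − r)/d² = (0.4805/0.1133) × (0.5/2.25) = 0.943
- n = (1.960 + 0.842·√B)²/A = 68.09, so 69 cases, as stated

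With 23 control-window cases at 10 per 1000 person-years, 23/(0.010 × 8/365.25) = 105,009 vaccinees, against 105,010 in Table 9. A Wald interval of ±10% at a PPV of 80%, with finite-population correction, gives 62 charts against 63 in Table 3. The plan has no arithmetic error that matters here. The issue is what the 69 cases and the PPV represent.

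**2. What the gate measures.** Let t be the PPV under the tracing rule and s the share of confirmed cases that are truly new-onset. The documents do not give s. The PPV for new-onset AF is t × s.

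- t = 80%, s = 95%, 90%, 80%: new-onset PPV 76%, 72%, 64%
- t = 90%: a new-onset PPV of 80% needs s ≥ 0.80/0.90 = 89%

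**3. Effect on the IRR if the extra cases are unrelated to vaccination.** Let q be the assumed share of counted cases that are not new-onset, with RR 1 and an even spread over the two windows. With a true RR of 2, the share of cases in the risk window is p = (1 − q)(2/3) + q/2, and the apparent RR is p/(1 − p). Power with n cases is Φ[(√(nA) − 1.960)/√B], with A and B taken at the apparent RR.

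| q (assumed) | p | Apparent RR | Power, 69 cases | Cases for 80% power |
|---|---|---|---|---|
| 0 | 0.667 | 2.00 | 80.5% | 69 |
| 10% | 0.650 | 1.86 | 71% | 85 |
| 20% | 0.633 | 1.73 | 61% | 108 |
| 30% | 0.617 | 1.61 | 50% | 142 |

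**4. Direction if they are not unrelated.** Give the non-new-onset cases their own ratio R. Then p = (1 − q)(2/3) + q·R/(1 + R). The apparent RR falls below 2 when R < 2 and rises above 2 when R > 2.

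The only relevant counts are in Section 5, for serious AF within 30 days in the pivotal trial: 7 events (vaccine) against 1 (control), of which 2 against 1 were new-onset. By subtraction, 5 against 0 were not new-onset. These counts are tiny and precede any look-back, so they estimate neither q nor R. They do not, however, support fixing R at 1. Coding of old AF at visits linked to vaccination would also push cases into the early window.

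**The case against.** The strongest reply is that incidence is already handled at the claims step. Charts are drawn only from vaccinees who meet the algorithm, so a patient with a Table 7 code in any setting in the prior 365 days never reaches chart review. That stands. A reader might infer that any patient with known AF and a routine ECG becomes a confirmed new-onset case; the documents do not support this. A reader might also infer that the gate tests the wrong thing. It tests a necessary part, presence of AF, and omits the rest.

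Second, dilution towards 1 is not established. That also stands, as step 4 shows.

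Third, the power figures belong to 69 cases. Under Section 7.7.3 all claims-identified cases enter once the PPV reaches 80%, and Table 3 considers 1,000 to 100,000 identified cases. At such numbers the power loss largely disappears, and what remains is bias in the estimate. The figures apply most directly to the chart-confirmed branch, whose target is 69.

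Fourth, the event-identification cell for AF is redacted, and the adjudication forms are separate documents that might collect onset. This limits what can be said about the forms. It does not change the confirmation criterion in Section 7.3.2.4, which would still confirm AF that is not new.

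Fifth, the count of codes more than 365 days old, the optional PPV adjustment and the optional quantitative bias analysis (Section 7.9) all help. The count exposes part of the problem, but it changes neither case status nor the PPV, and the other two are not commitments.

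**Conclusion.** The point holds in limited form. The protocol defines the outcome and the 80% gate for new-onset AF, while its confirmation rule verifies AF only. AF coded solely outside Table 7, or solely more than 365 days before the event, can therefore be counted as confirmed new-onset AF in either branch, and the measured PPV is an upper bound for the PPV of interest.

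The size is conditional. The 72% and 64% figures rest on assumed new-onset shares of 90% and 80%. The apparent RR of 1.86 to 1.61 rests on an assumed 10% to 30% share with no vaccine effect and an even spread over the windows; power of about 71% to 50% further assumes that only 69 cases are analysed. The documents give neither the share nor the sign of the bias, and they do not list the other AF codes, so how much the two-code look-back misses cannot be sized.

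AF is a secondary outcome, but Table 10 puts its inferential analysis first and the validation falls in the early monitoring queries, so the definition should be settled before charts are adjudicated.

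**What to change.** - **Section 7.3.2.4:** define confirmed new-onset AF as AF on a tracing plus no AF documented in the reviewed record before the index event. Compute the 80% gate on that definition.
- **Section 7.3.2.4:** have the adjudicator record the AF onset date, and use it in the chart-confirmed branch.
- **Table 4:** widen the AF outcome-free screen to all AF codes, leaving the event codes in Table 7 unchanged.
- **Section 7.7.2.3:** add a sensitivity analysis that drops cases with an AF code more than 365 days earlier. These cases are already flagged.

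The cost is small: one added criterion and one onset field on a form that already collects admission, discharge and cardiology notes, a code-list edit, and one extra run. The downside is that the measured PPV may fall, which makes the chart-confirmed branch, with its extra chart retrieval, more likely.
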